#### **Objective(s)**

### 2.1 **Primary Objective**

Aim 1. To confirm whether that highly-trained swimmers experience EIAH

It is hypothesized that highly-trained swimmers will experience EIAH, as evidenced by a decrement in peripheral capillary oxyhemoglobin saturation  $(S_pO_2)$  of 5% or greater from rest to submaximal and/or maximal exercise.

Aim 2. To test whether a pharmacological agent that is a competitive inhibitor to histamine (cetirizine HCI) can improve nadir  $S_pO_2$  during submaximal (70 and/or 85%  $\dot{V}O_{2max}$ ) and/or maximal (100%  $\dot{V}O_{2max}$ ) exercise.

It is hypothesized that the pharmacological agents will significantly (p < 0.05) increase nadir SpO2 during all exercise intensities. This will be assessed using a linear mixed model including random effects for subject, subject within-treatment, and subject within-intensity to account for the repeated measures design. Treatments (placebo and cetirizine HCI), intensity (70, 85, and 100% of  $\dot{V}O_{2max}$ ), and the interaction between treatment and intensity will be included. Main effects and interactions will be tested using *F*-tests from a two-way ANOVA.

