#### 2.2 Secondary Objective

Aim 3. To test whether degree of desaturation from rest to maximal exercise  $(\Delta S_pO_{2,rest}-S_pO_{2,100\%})$  is correlated with the magnitude of histamine release from rest to maximal exercise  $(\Delta \% H_{rest}-\% H_{100\%})$ .

It is hypothesized that degree of saturation and histamine release will be significantly (p < 0.05) correlated. Correlational strength will be assessed via Pearson correlation coefficient.

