- Graded exercise test: After a self-determined warm-up and a rest period of at least 2 minutes, a progressive maximal exercise test will be performed in a specially constructed, customized variable water flow pool (Endless Pools, Aston, PA, USA), with subjects swimming against a flow rate of approximately 1.5 m·s for men and 1.31 m·s for women tethered to a pulley with a 1.2 and 1 kg mass, respectively. After two minutes, the tethered mass will be increased by 0.2 kg every two minutes until each subject reaches volitional exhaustion. Metabolic and ventilatory variables and SPO2 will be measured as described below. Subjects' heart rates during the tests will be continuously recorded (Cardio Swim HR Monitor; Freelap, Switzerland). VO2MAX will be considered as the maximal value attained during the test, provided at least two of three criteria are met, which will include an RER of greater than 1.05, achievement of 90% of age-predicted maximal heart rate, and an increase in VO2 of less than 0.15 L/min over the previous workload. Plasma histamine, whole blood histamine, and histamine release will be measured before and after this test as previous.
- Constant load tests: Following the maximum exercise test, subjects will perform constant load swimming exercise at approximately 70 and 85% of subjects' previously recorded HRMAX during that session. The tethered mass used to elicit the workloads will be estimated during the first 20-minute rest period by performing a linear regression between HR and tethered mass to approximate the tethered mass that would elicit 70 and 85% of maximum HR. Subjects will swim for 5 minutes. Metabolic and ventilatory variables and SPO2 will be measured as described below. Plasma histamine, whole blood histamine, and histamine release will be measured following these tests as previous.
- Drug administration An opaque sugar-free gelatin capsule (Capsuline, Dania Beach, Florida, USA) will be administered 60 minutes prior to testing and will either be empty (placebo) or contain CH (10 mg; Zyrtec®; Johnson & Johnson, New Brunswick, NJ, USA) according to the visit condition.

Timeline of procedures:

Screening Visit (Visit 1): Once participants arrive at the laboratory, an investigator will
obtain written informed consent after all procedures and study risks are fully explained

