- Experimental Trials (visits 3 and 4): Prior to all testing sessions, participants will be asked to abstain from allergy medication for 48 hours, intense exercise for 24 hours, caffeine and alcohol for 12 hours, and food for 2 hours. Prior to the sessions 3-4, participants will also be asked to consume a similar diet the night before and day of each testing session. Women participants will be asked to self-identify when their last menses occurred. In order to prevent sex differences caused by fluctuations in hormone across the menstrual cycle, women participants will only be tested during the first 7 days following menstruation (when estrogen and progesterone hormones are at their lowest levels) for sessions 2-4 (Allen et al., 2016). Apart from receiving a placebo (PL) or drug treatment (CH) prior to exercise, participants will perform identical protocols on each visit to the laboratory. Participants will report to the lab and consume either a placebo or CH pill, followed by a health history update questionnaire and their resting pulmonary function will be measured. Participants will then complete a self-selected warm-up that will be standardized across the two testing sessions, followed by instrumentation. The exercise protocol beings with a progressive swimming test to maximum aerobic capacity (VO2max) in a swimming flume, followed by two constant load work bouts at approximately 70 and 85% of the previously recorded HRmax while peripheral capillary oxyhemoglobin saturation ( $S_pO_2$ ) is continuously monitored. Participants will receive a 20-min break between each work bout. Drug treatments will be assigned in a double-blind, randomized crossover fashion such that each participant receives each treatment. Concentrations of plasma histamine, whole blood histamine, and histamine release will be assessed from a venous blood draw one hour prior to commencement of the aerobic capacity test, and immediately following the aerobic capacity test and each of the two constant load bouts.

**8.0 Study Calendar** The following procedures will be undertaken during the visits.

Table 1: Description of Stud	v Procedures that will take	place on each visit to the laboratory.
	y i roccuures that will take	

STUDY PROCEDURES	Screening (Visit 1)	Selection Exercise Test (Visit 2)	Experimental Trials – Randomized Crossover (Visits 3-4)	
			Placebo	Cetirizine HCI
Height	Х		Х	Х
Weight	Х		Х	Х
Heart rate	Х		Х	Х
Urine specific gravity		Х	Х	Х

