Blood pressure	Х			
Health history questionnaire	Х			
Health history update questionnaire		X	Х	Х
Pulmonary function	Х		Х	Х
Complete blood count		X		
Plasma IL-1β		X		
Plasma IL-8		X		
Plasma histamine		Х	Х	Х
Whole blood histamine		Х	Х	Х
Histamine release		Х	Х	Х
Selection exercise test		X		
Peripheral capillary oxyhemoglobin saturation			Х	Х
Indirect calorimetry			Х	Х
Graded exercise test			Х	Х
Constant load tests			Х	Х
Placebo pill			Х	
Cetirizine HCI pill				Х

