In order to test for potential differences in the dependent variables of interest, linear mixed models will be used including random effects for subject, subject within-treatment, and subject within-intensity to account for the repeated measures design. Treatment (PL and CH), intensity (70, 85, and 100% of  $\dot{V}O_{2max}$ ) and the interaction between treatment and intensity will be included. Main effects and interactions will be tested using *F*-tests from a two-way ANOVA. Statistical significance will be assessed using a pre-determined  $\alpha$  level of 0.05. Where significant main effects or interactions are observed, estimated marginal means will be used to test for differences in the drug conditions and adjusted for multiple comparisons using Dunnett's method.

*Hypothesis* 3. The correlation between the change in histamine release ( $\Delta$ %Hpre-%Hpost) and the change in SPO2 at  $\dot{V}O_{2max}$  ( $\Delta$ SPO2rest-SPO2@100%) will be assessed in the pooled experimental and control cohorts (n=12) by a Pearson correlation coefficient using a predetermined  $\alpha$  level of 0.05.

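### The cetirizine-placebo model makes no use of the pre-exercise histamine values drawn at each crossover visit, which can cost precision but does not make the test invalid

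*Combined protocol and SAP*

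**What the plan says.** Section 12.0 (Hypothesis 2) states that "linear mixed models will be used including random effects for subject, subject within-treatment, and subject within-intensity to account for the repeated measures design". The fixed effects are treatment, the three exercise intensities, "and the interaction between treatment and intensity will be included". Section 2.1 gives the same model for Aim 2, which asks whether an agent that "is a competitive inhibitor to histamine (cetirizine HCI) can improve nadir" SpO2. The only further term allowed for is a visit-order regressor, added if a carry-over effect is seen.

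Pre-exercise information is available at both crossover visits:

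- **Histamine.** Under Experimental Trials in Section 7.0, the three histamine measures (percentage release, plasma and whole blood) "will be assessed from a venous blood draw one hour prior to commencement of the aerobic capacity test". Further draws follow each of the three bouts. Section 3.1 lists all three measures as primary outcomes.
- **SpO2.** Table 1 marks "Peripheral capillary oxyhemoglobin saturation" for the placebo and the cetirizine visit. A resting reading is not scheduled separately, but Aim 1 needs one (a fall "of 5% or greater from rest to submaximal and/or maximal exercise"), and so does Aim 3 ("To test whether degree of desaturation from rest to maximal exercise").

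On timing, Section 7.0 (Drug administration) places the capsule 60 minutes before testing. Under Experimental Trials, swimmers take it on arrival, and pulmonary function, warm-up and instrumentation follow.

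**The concern.** Each swimmer receives each treatment at one visit only, so the subject-within-treatment effect is the same thing as a subject-by-visit effect. Anything that moves a whole visit, such as assay level, hydration, training state or placement of the forehead sensor, moves all three intensities together. Averaging over intensities does not remove it, and it enters the error against which the treatment effect is tested. The visits may be up to 60 days apart.

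A pre-exercise value from the same visit can carry part of that shift. The plan collects such values and does not use them in the drug comparison. With at most 12 within-swimmer differences, avoidable variance matters. It matters most for histamine: three of the five primary outcome measures are histamine measures, and the model as written has no pre-exercise level of intensity, change score or covariate for them.

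**Working it through.** **1. The plan's own figure.** Section 12.0 gives Cohen's f = 1.22, alpha 0.05, power 0.80 and 12 subjects, from a fixed-effects ANOVA routine. The noncentrality is f² × N = 1.4884 × 12 = 17.86, with numerator df 1. With the eight cells of the 2 × 4 source table (denominator df 4), power is 0.764 at N = 11 and 0.878 at N = 12, so 12 reproduces. With the trial's own six cells, power at 12 is 0.937. The calculation contains no visit-level variance term, so it says nothing about the size of the present issue.

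**2. Gain from adjustment.** Average each visit over the three intensities and take the cetirizine minus placebo difference for each swimmer. In balanced data this gives the planned treatment test. Let σ² be the variance of that difference, and r its correlation over swimmers with the same difference before exercise. For normal data with no drug effect on the pre-exercise value:

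- planned: σ²/n
- adjusted: (σ²/n)(1 - r²)(1 + 1/(n - 3))
- ratio at n = 12: (1 - r²) × 10/9

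| r | Ratio, n = 12 | Ratio, n = 8 (factor 6/5) |
|---|---|---|
| 0 | 1.11 | 1.20 |
| 0.32 | 1.00 | 1.08 |
| 0.41 | 0.92 | 1.00 |
| 0.5 | 0.83 | 0.90 |
| 0.7 | 0.57 | 0.61 |

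At n = 12, r = 0.5 is worth 12/0.833 = 14 swimmers and r = 0.7 is worth 12/0.567 = 21. Error df fall from 11 to 10, and the critical t rises from 2.20 to 2.23. The n = 8 column is shown because Section 12.0 targets eight swimmers with EIAH plus four controls, and states pooling to 12 only for Hypothesis 3.

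**3. SpO2 under assumed SDs.** The documents give no within-swimmer SD. Assume an error SD of 1.5 points per exercise reading, 0.5 to 1.0 for the resting reading, and a visit shift of SD s shared by rest and exercise. The planned SE is √[2(s² + 1.5²/3)/12]; the adjusted SE applies the ratio above. Power is simulated with 40,000 runs per case.

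| s | Planned SE | Adjusted SE | Power for 1.6 points, planned | Power for 1.6 points, adjusted |
|---|---|---|---|---|
| 0 | 0.35 | 0.37 | 0.98 | 0.97 |
| 1 | 0.54 | 0.42-0.48 | 0.77 | 0.85-0.93 |
| 2 | 0.89 | 0.43-0.54 | 0.38 | 0.77-0.92 |

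Table 2 of the plan shows differences of 2.8, 2.8, 2.8 and 4.4 points, mean 3.2; 1.6 is half of that. At 3.2 points the planned analysis has power of at least 0.90 in every scenario tried.

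**4. Validity.** With the planned subject-within-treatment effect, simulated type I error is 0.049 to 0.051 for s from 0 to 2. Without that term it would be 0.08 to 0.26 for s from 0.5 to 2. The plan includes it.

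**5. Post-dose rest.** If the drug raised resting SpO2 by 0.5 points (s = 1, resting error SD 0.5), the covariate slope is 1/(1 + 0.25) = 0.8. The adjusted effect becomes 1.6 - 0.8 × 0.5 = 1.2. A plain change from rest would give 1.1.

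**The case against.** The strongest reply is that nothing in the plan is wrong. Nadir SpO2 in a randomised crossover is a legitimate target, each swimmer is their own control, and the planned random effect keeps the test valid. The plan also limits day-to-day variation by abstention rules, similar diet, menstrual timing, a repeated warm-up and a secured sensor. The benefit rests wholly on r, which is unknown; below 0.32 (0.41 with eight swimmers) adjustment loses precision. At the effect size in the plan's Table 2, power is ample anyway. Resting SpO2 follows the capsule, so conditioning on it could remove part of the drug effect. All of this stands, and for SpO2 it decides the matter in favour of keeping the unadjusted model primary.

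On histamine, the reply is that Aim 2 concerns SpO2 only, and that Section 12.0 does not say on which scale the histamine outcomes are compared between drugs. That is so. But the model is stated for the outcomes of interest generally, histamine measures are named as primary outcomes, and the intensity factor has no pre-exercise level. Whatever was intended, the use of the pre-exercise value is not specified. The order of draw and capsule is also unstated, since both fall about one hour before exercise. That can be settled in one line and does not remove the point.

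Three stronger readings are tempting and are not supported. A reader might infer that visit shifts bias the drug contrast or raise the false-positive rate: randomised order and the subject-within-treatment effect rule this out. A reader might see Aim 2 as inconsistent with Aims 1 and 3: those aims ask about desaturation from rest, and Aim 2 asks a different question. And adjustment is not the only precision gain open without more swimmers; an unconditional visit-order term could also remove variance.

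**Conclusion.** The omission is confirmed and its consequence is lost precision. For the histamine outcomes adjustment is worth prespecifying: the pre-exercise draw falls at about dosing time, so it is in effect a pre-drug baseline, and the data are already collected. For nadir SpO2 it is worth only a sensitivity analysis.

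The size cannot be fixed from the documents. With 12 swimmers the variance of the drug effect would change by a factor between 1.11 (r = 0) and 0.57 (r = 0.7). This assumes approximately normal differences, no drug effect on the pre-exercise value and all 12 swimmers in the analysis. The SpO2 power figures also rest on the assumed SDs. Table 2 concerns diphenhydramine in male runners, so power at 3.2 points is reassuring only if cetirizine in swimmers of both sexes does as well.

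**What to change.** - **Histamine outcomes.** Add to the Hypothesis 2 model the visit's own pre-exercise value of the same measure (plasma, whole blood or percentage release), entered as its deviation from the swimmer's two-visit mean. In that form the slope reflects differences between visits within a swimmer and is not mixed with differences between swimmers.
- **Order of draw and capsule.** State in Section 7.0 that the pre-exercise blood is taken before the capsule is swallowed.
- **Nadir SpO2.** Keep the planned unadjusted model as primary. Prespecify the model with resting SpO2, in the same deviation form, as a sensitivity analysis, and report the cetirizine-placebo difference at rest beside it. Schedule the resting reading explicitly. Do not substitute a plain change from rest: with no shared shift and a resting error SD of 1.0, power for a 1.6-point effect falls from 0.98 to 0.77, against 0.97 with the covariate.

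The cost is a few sentences, one degree of freedom, and up to 11% more variance if the pre-exercise value proves uninformative (20% if only eight swimmers are analysed). The text should be in place before unblinding; added afterwards it would be a post hoc choice.

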### Table 2: SaO2ear data from Coyle, 2001

A two-way (treatment x intensity) ANOVA using these data produced a Cohen's *f* of 1.22 for the treatment main effect. Therefore, it was determined that using an a priori  $\alpha$  value of 0.05, an estimated twelve subjects are necessary to achieve a power of 0.80. The sample size calculation was conducted using G\*Power 3.1.9.7 (ANOVA: Fixed effects, special, main effects and interactions). Due to the randomized crossover design, all twelve subjects (n = 6 men, n = 6 women) will complete all experimental treatments (PL and CH) at all intensities (70, 85, and 100% of  $\dot{VO}_{2max}$ ).

Previous investigations (Anselme et al., 1994; Mucci et al., 2001) have observed a strong, positive, and significant (r > 0.7; p < 0.05) correlation between  $\Delta$ %H ( $\dot{V}O_{2max}$  - rest) and  $\Delta P_aO_2$  (rest -  $\dot{V}O_{2max}$ ). Using a regression equation ( $\Delta$ %H = 0.0444( $\Delta P_aO_2$ ) - 0.1137; r = 0.80) from Anselme and colleagues (1994), a conservative estimate that a  $\Delta P_aO_2 > 10$  mmHg represents EIAH (Prefaut et al., 2000), we intend to recruit participants for the experimental trials who experience a  $\Delta$ %H > 0.33 during the Selection Exercise Protocol. However, should this inclusion criterion not be met by at least eight subjects, those experiencing the highest  $\Delta$ %H during the Selection Exercise Protocol will be recruited instead.

For proof of principle that EIAH can be prospectively identified using  $\Delta$ %H, a small control group (n=2 men, n=2 women) will also be recruited. For this group, we intend to recruit participants who exhibit the lowest  $\Delta$ %H during the Selection Exercise Protocol. These participants will complete both conditions of the experimental trials.

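### Dunnett's method adjusts nothing when there is one drug and one placebo, so cetirizine comparisons at 70, 85 and 100% would carry no multiplicity control, and Aim 2 has two different success rules

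*Combined protocol and SAP*

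**What the plan says.** Section 12.0, Hypothesis 2, fits a linear mixed model with two treatment levels and three intensity levels, "Treatment (PL and CH), intensity (70, 85, and 100% of" maximal oxygen uptake, plus their interaction. Each effect is F-tested at 0.05. The follow-up rule is: "Where significant main effects or interactions are observed, estimated marginal means will be used to test for differences in the drug conditions", and these are then "adjusted for multiple comparisons using Dunnett's method".

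The rule leaves two things open: whether the drug comparison is made at each intensity or once, pooled over intensities, and whether a significant intensity effect alone is enough to start it.

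Section 2.1 frames the same question in two ways. Aim 2 asks about nadir saturation "during submaximal (70 and/or 85" percent of maximum, joined by a second and/or to maximal exercise. The hypothesis beneath it expects an increase "during all exercise intensities".

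The sample size rests on the treatment main effect alone: a Cohen's f "of 1.22 for the treatment main effect", from which, with an alpha "value of 0.05, an estimated twelve subjects are necessary to achieve a power of 0.80".

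**The concern.** Dunnett's method protects against comparing several treatments with one control. This trial has one treatment and one control. Its multiplicity, if any, lies across the three intensities, and the named method does not address that direction. A reader of the final report would believe that an intensity-specific result had been adjusted when it had not.

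Aim 2 as worded allows success to be claimed at a single intensity, while its hypothesis requires all three. The choice between these rules could then be made after the data are seen.

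The screening F-tests may give little protection. Saturation is expected to fall with effort whether or not the drug works (Table 2, placebo: 93.7% at 70% effort, 89.8% at 100%). If the intensity effect counts as a trigger, the drug comparisons will almost always be run.

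**Working it through.** **The plan's own figure.** Noncentral F with λ = f²N, df1 = 1, df2 = N − cells. Table 2 has 4 intensities × 2 treatments = 8 cells. At N = 12, λ = 1.22² × 12 = 17.9, df2 = 4 and power is 0.878; 12 is the smallest N reaching 0.80. The stated 12 reproduces. With this trial's own 6 cells the minimum is 10 (power 0.818), and power at 12 is 0.937. This is one F-test at 0.05, so multiplicity does not touch it.

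**Dunnett with one comparison.** Number of comparisons = treatment levels − 1 = 2 − 1 = 1. A numerical check on one data set gave p = 0.3646 from Dunnett and 0.3648 from the t-test; the difference is integration error.

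**Three by-intensity tests at 0.05, no drug effect.** If independent, 1 − 0.95³ = 0.143. The three differences come from the same swimmers, so they may be correlated. The documents give no value, so ρ is assumed. Simulated paired t-tests, n = 12:

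| ρ | any two-sided p < 0.05 | any significant benefit | first Holm step |
|---|---|---|---|
| 0 | 14.2% | 7.4% | 4.9% |
| 0.25 | 14.0% | 6.9% | 4.8% |
| 0.5 | 12.8% | 6.5% | 4.6% |
| 0.75 | 10.8% | 5.4% | 4.0% |

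The nominal rate for one test in the beneficial direction is 2.5%. Model-based marginal means give slightly lower two-sided rates (13.6% at ρ = 0, 10.5% at 0.7, 9.5% at 0.8).

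**Adding the F-test screen, no drug effect, n = 12.**

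- *Any main effect or the interaction opens the comparisons.* Assumed: intensity means 93.7, 93.2 and 89.8 (the middle one interpolated), SD 2.5, half the variance between subjects. The intensity test was significant in essentially every run. The two-sided rate was 14.4, 13.8, 12.9 and 10.9% at ρ = 0, 0.3, 0.5 and 0.75. With half that gradient it was 13.8, 13.3, 12.6 and 10.7%. This screen protects almost nothing.
- *Only treatment or interaction opens them.* Two-sided 5.8-6.4%, beneficial direction 2.9-3.4%. Across both ways of testing, and ρ up to 0.8, the two-sided range is 5.7-6.7%; for n from 8 to 16 it is 5.5-7.0%.

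**Drug truly works at 100% only**, with the treatment-or-interaction screen. The screen opens in 81-100% of trials, and a false result at 70 or 85% appears in 8.3-9.5% (two-sided, ρ from 0 to 0.7), or 4-5% in the beneficial direction. The stricter screen helps less here because the real effect opens it.

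**With the correction.** Bonferroni over three, which has the same familywise error as Holm when there is no effect anywhere, gives 3.4-3.5% with the treatment-or-interaction screen (ρ from 0 to 0.7).

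**The case against.** The best defence is that the plan does not commit to three tests. It speaks of differences between drug conditions, which fits one pooled placebo-cetirizine contrast. That contrast runs at 0.05 with no inflation. Nor would there be inflation if success required all three intensities, as the hypothesis says. Drug comparisons prompted by an intensity effect would be an unusual use of a post-hoc rule, and the text does not say outright that this is intended. The by-intensity contrasts are follow-ups to a main-effect test that is sound, and Holm is one acceptable choice among several.

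Much of this stands. By-intensity testing is an inference from the interaction term and from Aim 2, and the loose trigger is the literal reading but not a stated one. The defence does not rescue the Dunnett sentence: on the pooled reading too there is one comparison and nothing to adjust.

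A reader might infer that the chance of falsely claiming that cetirizine works at some intensity is simply 11-14%. The documents do not support that. The figure is two-sided, whereas the hypothesis is an increase; it also needs the loose trigger. The corresponding rate in the beneficial direction is 5-7%.

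A reader might also divide 11-14% by the rate for all three tests showing benefit under no effect (0.5% or less) and conclude that the two success rules differ more than 20-fold. That sets a two-sided rate against a one-sided one, in the situation most favourable to the stricter rule. If the drug works at two intensities but not the third, the all-three rule falsely succeeds in 2.5% of trials. Against 7.4% for benefit at any intensity, the gap is about 3-fold.

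**Conclusion.** The point holds with limits. It is certain that Dunnett's method has no effect with these two conditions, that no other adjustment across intensities is named, and that Aim 2 and its hypothesis state different success rules.

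The size of the error depends on what the plan leaves unsaid. If contrasts are made at each intensity, the two-sided error is 11-14% under the literal trigger, about 6% under a treatment-or-interaction trigger, and about 8-10% at 70 or 85% when the drug works only at 100%. In the beneficial direction these are 5-7%, about 3% and 4-5%, against a nominal 2.5%. All rest on 12 swimmers and an assumed correlation of 0 to 0.75; at 0.8 the literal-trigger rate is about 10%.

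The plural for the drug in the Aim 2 hypothesis and the reference in section 13.0 to a fifth visit suggest that Dunnett may survive from a design with more active arms. They do not prove it. This should be corrected before analysis, but it does not undermine the main-effect test.

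**What to change.** Replace the Dunnett sentence in section 12.0 with:

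> The treatment main effect is the confirmatory test of Aim 2. If the treatment main effect or the treatment-by-intensity interaction is significant, placebo-cetirizine differences at 70, 85 and 100% are estimated with 95% CIs and tested with Holm adjustment across the three intensities.

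State that a significant intensity effect alone does not open the drug comparisons. Use one success criterion in Aim 2 and its hypothesis.

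This changes wording only. The cost is power at single intensities if the true effect is well below that in Table 2. At 100% effort, reading the table's ± values as SDs and assuming a within-subject correlation of 0.5, the difference is 94.2 − 89.8 = 4.4 and its SD is √(3.1² + 1.8² − 2 × 0.5 × 3.1 × 1.8) = 2.70. With n = 12, power falls from 0.999 at 0.05 to 0.993 at the strictest Holm step (0.05/3). With half the effect it falls from 0.73 to 0.53.

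### Hypothesis 3 reports a Pearson r as the strength of association in 12 swimmers chosen for high or lowest histamine release, so r may overstate the correlation among the swimmers screened

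*Combined protocol and SAP*

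**What the plan says.** Section 2.2 (Aim 3) predicts an association: "It is hypothesized that degree of saturation and histamine release will be significantly (p < 0.05) correlated". It names the measure of its size: "Correlational strength will be assessed via Pearson correlation coefficient".

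Section 12.0 sets out who supplies the data. For the high group, "we intend to recruit participants for the experimental trials who experience a" change in %H above 0.33 at the Selection Exercise Protocol (Visit 2). There is a fallback: "should this inclusion criterion not be met by at least eight subjects, those experiencing the highest" change are taken instead. In addition, "a small control group (n=2 men, n=2 women) will also be recruited", and "For this group, we intend to recruit participants who exhibit the lowest" change in %H at the same visit.

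Under Hypothesis 3, Section 12.0 computes r in the "pooled experimental and control cohorts (n=12) by a Pearson correlation coefficient", at an alpha of 0.05. Section 5.0 also gives 12 as the number selected for the trials, so the consistent reading is 8 high plus 4 low. Section 7.0 measures SpO2 only in the flume trials, so r cannot be computed in all the swimmers screened. The plan has no slope, no range correction and no statement of the population to which r applies.

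**The concern.** A Pearson r depends on how widely the explanatory variable is spread in the sample. Taking swimmers from the top and the bottom of a distribution and leaving out most of the middle increases that spread. The same underlying relation then produces a larger r than it would in an ordinary group of highly-trained swimmers.

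Here the selection variable is the Visit 2 counterpart of the variable that enters the correlation. What is at stake is the size of the histamine-desaturation link, which is the mechanistic message of Aim 3. A reader who takes r as the correlation in highly-trained swimmers could be given too strong an impression.

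**Working it through.** **The plan's own figures reproduce.** The cut-off is 0.0444 × 10 − 0.1137 = 0.3303, stated as 0.33. The chance of at least 8 swimmers with EIAH among 26 at 50% prevalence is 0.9855, stated as >95%. The plan gives no power or expected r for Hypothesis 3.

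**Inputs from the documents (Section 12.0).** 26 screened (13 men, 13 women); 12 analysed, of whom 4 are controls (2 per sex), leaving 12 − 4 = 8 high (4 per sex).

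**Assumptions.**
- Changes are jointly normal and linearly related, signed so that a larger rise in %H goes with a larger fall in SpO2.
- q, the correlation between Visit 2 and flume change in %H, is not given; 0.5 to 1.0 is used.
- The share of swimmers above 0.33 is not given. About half is used, following the 50% prevalence: 26 × 0.5 = 13, taken as the upper 7 of 13 per sex.
- Visit 2 %H says nothing about desaturation beyond what flume %H says (relaxed below).

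**Formula check, fallback rule.** Taking the top 4 and bottom 2 of 13 per sex makes the variance of Visit 2 change in %H 1.83 times that of the pool, an SD ratio of √1.83 = 1.35. For the flume variable the variance ratio is k² = 1 + q²(1.83 − 1), and

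r_selected = ρk / √(1 + ρ²(k² − 1)).

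With ρ = 0.5:
- q = 1: k = 1.353; 0.676 / √1.2075 = 0.62.
- q = 0.5: k² = 1 + 0.25 × 0.83 = 1.2075, k = 1.099; 0.549 / √1.0519 = 0.54.

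The SD of the flume variable therefore grows by about 35% at q = 1 but only about 10% at q = 0.5. The formula ignores the slight downward bias of r at n = 12, so simulated means are a little lower.

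**Simulated mean r, n = 12 (at least 6,000 trials per setting).**

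| True r | Selection | q = 0.5 | q = 0.8 | q = 1.0 | Unselected 12 |
|---|---|---|---|---|---|
| 0.5 | 4 per sex at random from upper 7, plus lowest 2 | 0.505 | 0.533 | 0.564 | 0.48 |
| 0.5 | highest 4 plus lowest 2 per sex | 0.520 | 0.568 | 0.606 | 0.48 |
| 0.7 | 4 per sex at random from upper 7, plus lowest 2 | 0.705 | 0.728 | 0.758 | 0.68 |
| 0.7 | highest 4 plus lowest 2 per sex | 0.72 | 0.76 | 0.79 | 0.68 |

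At q = 0 there is no inflation. At a true r of 0, mean r is 0 and about 5% of tests reject.

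**Other cohort size.** Section 12.0 can also be read as 12 plus 4 controls. With n = 16 under the fallback rule and a true r of 0.5, mean r is 0.55 at q = 1 and 0.505 at q = 0.5, against 0.49 in 16 unselected swimmers.

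**Slope.** Under the assumptions above, with both variables in SD units, the mean slope stays at 0.50 and 0.70 throughout. Now let Visit 2 and flume %H be equally noisy readings of one trait that drives desaturation. Under the fallback rule with reliability 0.5, true slopes of 0.5 and 0.7 give mean slopes of 0.59 and 0.83. With reliability 0.8 they give 0.55 and 0.77.

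**Range correction.** r_c = ru / √(1 − r² + r²u²), where u is the Visit 2 SD in all screened swimmers divided by that in the selected 12. Under the fallback rule with a true r of 0.5, mean r_c is 0.51 at q = 1, 0.47 at q = 0.8 and 0.43 at q = 0.5.

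**The case against.** The strongest reply is that selection and analysis do not use the same measurement. Selection uses %H around the Visit 2 pool swim; Hypothesis 3 uses %H around maximal flume exercise. If the two correlate weakly there is little bias. This stands, and it is why the size cannot be fixed from the documents. The design does assume some link, because Section 12.0 uses Visit 2 %H to identify EIAH prospectively.

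Second, the larger figures need the fallback rule and near-perfect stability between visits. This also stands. Under the main rule with q = 0.5, mean r is about 0.51 for a true 0.5.

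Third, imprecision is larger than the bias. An observed r of 0.5 with n = 12 has a Fisher 95% CI of tanh(0.549 ± 1.96/√9), or −0.10 to 0.83. That is correct, but sampling error has no preferred direction, whereas this bias favours the hypothesis.

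A reader might also infer more than the documents support:
- *That the significance test is invalid.* It is not; its error rate stays at about 5% when the true correlation is zero.
- *That r will be judged against the cited r > 0.7.* Section 12.0 cites those correlations in deriving the 0.33 cut-off. They concern PaO2, not SpO2, and the stated criterion for Hypothesis 3 is p < 0.05.
- *That a slope removes the problem outright.* It does so only if Visit 2 %H adds nothing about desaturation beyond trial-day %H. Under the shared-trait model above, the slope is biased too.

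**Conclusion.** The point holds in a limited form. If the true correlation is positive and Visit 2 change in %H tracks flume change in %H, the planned r tends to overstate the correlation among the highly-trained swimmers screened, and nothing in the plan corrects or qualifies it.

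For a true r of 0.5 and q from 0.5 to 1.0, the excess over an unselected 12 is about 0.505 − 0.48 = 0.03 to 0.564 − 0.48 = 0.08 under the main rule. Under the fallback it is about 0.520 − 0.48 = 0.04 to 0.606 − 0.48 = 0.13. These sizes rest on the assumed q, on about half of those screened exceeding 0.33, and on normality and linearity. An unconditional claim that r is inflated, or by how much, is not supported.

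Severity is low: the aim is secondary, the selection and pooling are openly stated, and the test remains valid. It is a cheap improvement.

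**What to change.** In Section 12.0, Hypothesis 3 (and to match in Section 2.2):

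1. Report the regression slope of the SpO2 change on the change in %H, with its 95% CI, alongside r. The p-value is the same as for r = 0.
2. State that r describes a sample selected on histamine release and is not an estimate for all highly-trained swimmers.
3. Give a range-corrected r, using the Visit 2 SD of change in %H in all screened and in selected swimmers, as a sensitivity analysis only.
4. State the limits of both. The slope is free of selection bias only if Visit 2 %H adds nothing about desaturation beyond trial-day %H. The range correction over-corrects when Visit 2 and flume values correlate weakly.

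The cost is a few sentences in the plan and a few lines of analysis; no new data are needed. The downside is a less favourable headline r and slightly more to report.
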